## **7. CLINICAL, RADIOLOGICAL, LABORATORY AND SURGICAL EVALUATIONS**

### **7.1 Screening Evaluations**

- History and physical exam within 3 months prior to protocol enrollment.
- Baseline SHIM and EPIC 26 Scores within 3 months of RARP

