## 10. STATISTICAL CONSIDERATIONS

This is a blinded two-arm randomized phase 2 trial. Patients will be randomized in a ratio 1:1 to study arms, the experimental Arm I (membrane placement) and control Arm II (no membrane placement, standard of care surgery), using a permuted block design stratified by baseline SHIM score (<17 vs. >=17), and use of ANY erectile aids (Yes vs. No) in the last 3 months.

All analyses will be performed as an intention to treat and as per Protocol. Although there is no data to suggest an increased risk of any potential adverse effects with placement of a sling, we will monitor adverse events as per section 10.7.2. An interim analysis of the primary efficacy endpoint, change in SHIM score, will be performed as part of the analysis plan as described in section 10.7.3..

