### 10.2 Secondary Endpoints

- Among men with a SHIM greater than or equal to 17 at baseline, we will compare the proportion of men in each group with mild ED or better, defined by a SHIM greater than or equal to 17, at 3, 6, 9 and 12 months post RARP.

- Among men with a SHIM greater than or equal to 17 at baseline, we will compare the proportion of men in each group who are able to achieve an erection sufficient for intercourse more than 50% of the time at 3, 6, 9 and 12 months post RARP.
- Among men with a SHIM greater than or equal to 17 at baseline, we will evaluate the proportion of men in each group who require the use of more invasive erectile aids (intra-cavernosal injection, vacuum pump, or penile prosthesis) at 3, 6, 9, and 12 months post RARP.
- Rates of urinary control as measured by no pads per day at 3, 6, 9, and 12 months.

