## 10.6 Statistical Analysis

The difference in the SHIM score decline in each group from baseline to 12 months post RARP with 95% CIs will be reported as the primary endpoint for the study. Linear regression models will be fitted to determine the likely decline in SHIM scores based on receipt of a membrane during RARP. These models will control for baseline SHIM scores, age, and a binary indicator of the use of any oral erectile aids, in addition to other important demographic and clinic factors.

Among men with a SHIM greater than or equal to 17, the proportion of men in each group with a SHIM of 17 or greater, able to achieve an erection sufficient for intercourse more than 50% of the time, or not requiring any invasive erectile aids at each follow up interval will be reported and compared using counts and percentages with 95% CLs. Logistic regression models will be fitted to determine the likelihood of having achieving each result controlling for age and a binary indicator of the use of any oral erectile aids, in addition to other important demographic and clinic factors. Both unadjusted and adjusted odds ratios with 95% CIs and their corresponding p-values will be reported

In addition, we will report by treatment group adverse event rates by grade and attribution, and the number and percentage of men not needing pads.

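### Section 10.6 does not pre-specify baseline SHIM for the logistic models of the potency endpoints; naming it would give a small gain in power and settle the adjustment in advance

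*Combined protocol and SAP*

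**What the plan says.** All the relevant text is in the combined protocol and SAP.

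- **Primary linear model (10.6):** "These models will control for baseline SHIM scores, age, and a binary indicator of the use of any oral erectile aids".
- **Logistic models (10.6):** the named covariates are given as "controlling for age and a binary indicator of the use of any oral erectile aids". Baseline SHIM is not among them.
- **Both lists** then continue "in addition to other important demographic and clinic factors", without saying which factors or how they will be chosen. For the logistic models, unadjusted and adjusted odds ratios are both to be reported with p-values.
- **Population (10.2):** each of the three potency endpoints (SHIM of 17 or more, erection sufficient for intercourse more than half the time, need for invasive aids) is assessed "Among men with a SHIM greater than or equal to 17 at baseline".
- **Randomisation (10):** "stratified by baseline SHIM score (<17 vs. >=17), and use of ANY erectile aids (Yes vs. No) in the last 3 months".
- **Data collection (7.1):** "Baseline SHIM and EPIC 26 Scores within 3 months of RARP". The score is also in the Appendix I schedule, so it will be available for every analysed man.
- **Erectile aids:** 10.6 does not date its oral-aid indicator. Section 5.4 plans to record use at every follow-up so that it can be controlled for in the analysis. Section 6.2 excludes users of non-oral aids at entry.

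**The concern.** The first potency endpoint is a cut-off on the same scale as the covariate that is not named. A man who enters at 17 stays a responder only if he loses nothing, while a man who enters well above 17 has room to lose. Restricting the analysis to men at 17 or more does not remove this spread. Randomisation balances the arms either side of 17 but not within the range above it, so chance differences in baseline score inside the subset are corrected only if the model contains the score.

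Three things are at stake: some power, the size of the reported odds ratio, and the freedom to decide on adjustment for baseline SHIM after the data are in. The undated oral-aid indicator adds a related ambiguity. It could be read as use before randomisation or as use during follow-up, and follow-up use may itself be affected by how well erections recover.

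**Working it through.** **Plan's own figure.** The documents state no power or sample size for the logistic endpoints, so there is none to reproduce. The inputs below come from the primary-endpoint planning.

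**Inputs from the documents**
- Control decline in SHIM: mean 10; SD 8.5 observed, 9.8 pessimistic (10.5).
- Arm difference 3.80 (Table 10.1, row with SD 8). Section 10.5 also mentions a smaller difference, 2.68; that discrepancy is a separate matter.
- 70 men per arm (4.1); mean baseline SHIM 19 in the historical cohort (10.5).

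**Assumptions not in the documents**
- SHIM maximum of 25; normal change scores; decline independent of baseline unless stated otherwise; baseline uniform on 17 to 25 in the subset (SD 2.6).
- 35 to 70 men per arm in the subset. With a normal baseline of mean 19, cut at 16.5, an SD of 4, 5 or 6 puts 73%, 69% or 66% of men at 17 or more. That is 0.734 × 70 = 51, 0.691 × 70 = 48 or 0.662 × 70 = 46 per arm, so 50 is a reasonable central value.

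**Step 1. How prognostic is baseline SHIM in the subset?** For a control man starting at score b, the chance of staying at 17 or more is P(Z ≥ (10 − (b − 17))/SD).

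| | b = 17 | b = 25 | Odds ratio over 8 points | Per point (8th root) |
|---|---|---|---|---|
| SD 8.5 | P(Z ≥ 1.18) = 0.12 | P(Z ≥ 0.24) = 0.41 | 5.0 | 1.22 |
| SD 9.8 | P(Z ≥ 1.02) = 0.15 | P(Z ≥ 0.20) = 0.42 | 4.0 | 1.19 |

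**Step 2. Power under that mechanism.** Final scores were simulated with decline 10, SD 8.5, arm difference 3.8 and 50 men per arm (4,000 trials), and logistic models were fitted with arm only and with arm plus baseline SHIM. Power went from 37.3% to 39.5%, a gain of 2.2 points. Across the Table 10.1 effects with 35 or 50 per arm the gain was about 1 to 3 points. The median log odds ratio rose from about 0.75 to 0.81, that is, from exp(0.75) = 2.12 to exp(0.81) = 2.25. The two models disagreed on p < 0.05 in 6% to 9% of trials.

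If higher scorers lose more (slope of final on baseline 0.7 or 0.5), the gain fell to about 1.0 or 0.3 points. With 9% discordant verdicts, the simulation standard error of a gain is at most √(0.09/4,000) = 0.5 points, so the decimals should not be leaned on.

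**Step 3. Power with the plan's named covariates.** A second simulation set the odds ratio per baseline point directly and kept age and the oral-aid indicator in both models (3,000 trials per row; 50 per arm; response 30% vs 50%; age log-odds −0.5 per SD; 30% aid users with log-odds −0.5).

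| Odds ratio per point | Without SHIM | With SHIM |
|---|---|---|
| 1.0 | 55.3% | 55.6% |
| 1.1 | 55.2% | 55.5% |
| 1.2 | 55.2% | 56.7% |
| 1.35 | 54.6% | 59.2% |

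Over 35, 50 and 70 per arm, and response rates of 30% vs 50% or 20% vs 40%, the gain was +1.0 to +2.0 points at 1.2 and +4.1 to +5.5 at 1.35. Under the null, type I error was 4.9% to 5.4% without SHIM and 5.0% to 5.7% with it.

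**Step 4. Chance imbalance.** With 50 per arm and SD 2.6, the standard error of the difference in mean baseline is 2.6 × √(2/50) = 0.52 points. At 1.22 per point, an imbalance of that size moves the log odds ratio by 0.52 × ln(1.22) = 0.52 × 0.199 = 0.10, against an effect near 0.8.

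**The case against.** The strongest reply is that the plan does not leave baseline SHIM out. The logistic sentence continues "in addition to other important demographic and clinic factors", and baseline SHIM is a clinical factor. This stands against any claim of exclusion. It does not answer the lack of pre-specification: an unnamed factor can be added or dropped once results are known, and Step 2 shows the verdict can turn on that choice in 6% to 9% of trials.

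A reader might also infer that a stratification factor is missing from the model. That is not so. The stratum is SHIM below 17 against 17 or more, and it is constant among the men analysed. Only variation above 17 is at issue.

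A reader might expect a large power loss, such as 8 points (56% to 64% in a simulation with an odds ratio of 1.49 per point). The documents do not support this. Ratios of 1.35 and 1.49 per point mean 1.35⁸ = 11 and 1.49⁸ = 24 across the range, against 5.0 from the plan's own decline and SD.

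The threshold argument is mechanical only for the SHIM endpoint. Intercourse and invasive-aid use are different outcomes, and the documents give no event counts for them, so sparse data cannot be ruled out.

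Finally, because 6.2 excludes users of non-oral aids, the erectile-aid stratum is in effect oral-aid use, and the indicator in 10.6 may already be that stratum. Its timing is still unstated.

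**Conclusion.** The point holds as a gap in pre-specification with a small cost. Under the plan's own decline and SD, a scale maximum of 25, a uniform baseline over 17 to 25 and decline independent of baseline, omitting baseline SHIM costs about 1 to 3 points of power and moves the odds ratio slightly toward 1. The cost is less if higher scorers lose more, and about zero if the score is not prognostic above 17.

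It would be wrong to infer bias or an invalid test: randomisation protects the comparison, and simulated type I error stays near 5% either way. The endpoints are secondary and carry no power claim, and the primary model already names baseline SHIM. The change is worth making because the data are already collected and the model is improved at almost no cost.

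**What to change.** In 10.6:

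1. Name continuous baseline SHIM as a pre-specified covariate in the logistic model for SHIM of 17 or more at follow-up. Include it in the intercourse and invasive-aid models where event counts allow, with the rule for that stated in advance.
2. Define the erectile-aid covariate as the randomisation stratum, that is, use in the 3 months before randomisation, not use recorded at follow-up.
3. Replace the open-ended clause with a closed list of covariates.

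This is a sentence or two of text and needs no new data. The only downside is one more parameter per model, which may matter if invasive-aid events are few.

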## 10.7 Interim Monitoring

### 10.7.1 Role of the Research Team and the DSMC

The Research Team will continuously monitor study accruals and adverse events from both treatment arms. Patients will be monitored closely **during treatment and subsequently over 30 days** for any **adverse event** potentially related to treatment. All toxicities, regardless their grade, will be recorded in the patient case report form using NCI/CTEP Common Terminology Criteria for Adverse Events (CTCAE) version 4.03. In addition, a one interim analysis **of the primary efficacy endpoint** is planned in first 50% of study patients.

The Sylvester Comprehensive Cancer Center's Data and Safety Monitoring Committee (DSMC) will monitor this protocol according to the Cancer Center's DSM Plan. In its oversight capacity, the DSMC bears responsibility for suspending or terminating this study.

DSMC oversight of the conduct of this trial includes ongoing review of accrual, adverse event data, and interim analysis of response to treatment. The guidelines appearing in Sections 10.7.2, and 10.7.3 are offered for DSMC consideration in assessing accrual, adverse events, and response to treatment. In addition, the DSMC will review reports from all audits, site visits, or study reviews pertaining to this clinical trial and take appropriate action.

### 10.7.2 Safety: Early stopping due to adverse events

The interim monitoring guidelines for stopping due to adverse events appearing in this section will be applied separately to each arm

- If a treatment-related (possible, probable, or definite) death (grade 5 toxicity) occurs, enrollment will be suspended and continuation of the study will be reassessed by the DSMC.
- **Unacceptable adverse event** is defined as any grade 3, 4, or 5 treatment-related possible, probable, or definite) adverse event, excluding grade 3 xxxx revolved or down grade to grade 2 with 14 days.
- Unacceptable adverse event is expected to occur in no more than 10% of patients. If there is evidence that the true rate of unacceptable adverse event exceeds 15%, then accrual to the particular study arm should be suspended. Specifically, we suggest as a guideline for early termination of accrual to a particular arm a posterior probability of 90% or higher that the true rate exceeds 15%. The table below shows specific instances where this guideline is met, suggesting early termination, and due to evidence of excessive unacceptable adverse event.

Number of patients with unacceptable adverse event #	Patients evaluated for adverse event	Observed adverse event rate >=
3	4 to 7	43%
4	8 to 12	33%
5	13 to 17	29%
6	18 to 22	27%
7	23 to 27	26%
8	28 to 32	25%
9	33 to 38	24%
10	39 to 43	23%
11	44 to 48	23%
12	49 to 54	22%
13	55 to 60	22%
14	61 to 65	22%
15	66 to 69	22%

#: treatment-related (possible, probable, or definite) grade 3 or higher adverse event, excluding grade 3 xxxx revolved or down grade to grade 2 with 14 days.

To illustrate the stopping guidelines, suppose that 7 evaluable patients in the have been assessed for adverse event and 3 of them have experienced unacceptable grade 4 treatment-related adverse event. (See row 1 of the above table.) Under this circumstance, the observed rate of unacceptable adverse event is 43%, resulting in a posterior probability of 92.1% (not shown) that the true underlying rate exceeds 15%, thereby suggesting early termination.

Posterior probabilities for the above table are calculated under a weak prior beta distribution with parameters  $\beta_1 = 0.2$  and  $\beta_2 = 1.8$ , which corresponds to an expected rate of 10% based on very limited information, roughly equal to having studied 2 patients. This prior distribution implies also a priori chance of only 21.6% that true rate is 15% or greater

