#### **4.1 Accrual goal**

70 men will be allocated to each arm. The rationale for this number is provided in the sample size section of the statistical analysis (Section 10.5)

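### Three entries in the adverse-event stopping table (9 of 38, 12 of 54, 13 of 60) fall just short of the stated 90% posterior rule, and no minimum number of patients is given

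*Combined protocol and SAP*

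**What the plan says.** Section 10.7.2 sets a Bayesian guideline for unacceptable adverse events and applies it to each arm separately. The criterion is in the text: "we suggest as a guideline for early termination of accrual to a particular arm a posterior probability of 90% or higher" that the true rate is above 15%. The prior is a beta distribution with parameters 0.2 and 1.8, "which corresponds to an expected rate of 10% based on very limited information", and the section adds that it implies an "a priori chance of only 21.6% that true rate is 15% or greater".

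The table is introduced with the words "The table below shows specific instances where this guideline is met". Its rows run without a gap from 3 events in 4 to 7 patients up to 15 events in 66 to 69 patients. The rows that matter here are 9 events in 33 to 38 patients, 12 in 49 to 54, and 13 in 55 to 60. A worked example gives a posterior probability of 92.1% for 3 events in 7 patients.

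Section 4.1 fixes the arm size: "70 men will be allocated to each arm". Section 10.7.1 offers the guidelines to the DSMC for its consideration and gives the DSMC responsibility for suspending or terminating the study.

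**The concern.** The prior, the reference rate and the cut-off are all stated, so every table entry can be checked. An entry listed as meeting the guideline should have a posterior of at least 0.90, and three do not. At those three sample sizes, a DSMC member reading the table and one computing the posterior would reach different answers on whether the guideline is met.

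A second, separate gap is at the start. The text rule can be met with 2 or 3 evaluated patients, but the table begins at 4 and the section names no minimum. A reader who treats the table as the whole boundary would conclude that nothing can trigger before the fourth patient. A reader who applies the text would not.

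What is at stake is whether a prespecified safety guideline gives one answer at each sample size.

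**Working it through.** **Inputs, all from section 10.7.2 except the arm size (section 4.1):** prior Beta(0.2, 1.8); reference rate 0.15; cut-off 0.90; the table rows; 70 men per arm.

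**Formula.** With x events in n patients the posterior is Beta(0.2 + x, 1.8 + n − x). The quantity compared with 0.90 is P(rate > 0.15) under that distribution.

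**Step 1: reproduce the plan's own figures.**
- Prior, Beta(0.2, 1.8): P(rate > 0.15) = 0.2160. The plan states 21.6%.
- 3 of 7, Beta(3.2, 5.8): P(rate > 0.15) = 0.9210. The plan states 92.1%.

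Both agree, so the model is the one the plan describes.

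**Step 2: compare the table with the 0.90 rule at every n from 4 to 69.** The smallest x with posterior at or above 0.90 equals the table's x at all but three sample sizes:

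| n | Table x | Posterior at table x | Smallest x reaching 0.90 | Posterior at that x |
|---|---|---|---|---|
| 38 | 9 | 0.8953 | 10 | 0.9506 |
| 54 | 12 | 0.8998 | 13 | 0.9473 |
| 60 | 13 | 0.8950 | 14 | 0.9427 |

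The largest shortfall is 0.9000 − 0.8950 = 0.0050, or 0.5 percentage points. Each mismatch is one event at the last sample size of its row.

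**Step 3: look for a single rule that explains the table.** A cut-off of 0.895 reproduces every row from 4 to 69. All three entries above round to 90% at whole-percent precision. The closest case that the table leaves out, 11 of 49, has posterior 0.8939, which rounds to 89%. The table is therefore internally consistent with rounding to a whole percent.

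**Step 4: below 4 patients.** 2 of 2, Beta(2.2, 1.8), gives 0.9625. 2 of 3, Beta(2.2, 2.8), gives 0.9252. Both meet the text rule by more than rounding could explain, and neither has a row.

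**Step 5: effect on the chance of crossing.** The number of events was followed patient by patient up to 70, adding an event with probability p at each step and removing paths when they reach the boundary. This assumes that events are independent and that the boundary is checked after every patient.

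| True rate p | Table as printed | Only the three row ends changed | Full text rule |
|---|---|---|---|
| 10% | 6.4% | 6.3% | 7.8% |
| 15% | 27.7% | 27.2% | 29.2% |
| 20% | 62.6% | 62.0% | 63.7% |

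The full text rule adds 2 of 2 and 2 of 3, and also 15 of 70 (posterior 0.9069). Leaving out the 70-patient case changes 29.2% to 29.0% at a true rate of 15%.

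The chance of reaching 2 events within the first 3 patients is p² + 2p²(1 − p). At p = 0.10 this is 0.010 + 0.018 = 2.8%. At p = 0.20 it is 0.040 + 0.064 = 10.4%.

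**The case against.** The strongest defence is rounding. The cut-off is written as a whole percent, and one rule (0.895, shown as 90%) generates every row from 4 to 69. On this view the table is not miscalculated. That stands as the likely explanation, and it rules out reading the three entries as scattered errors or as the product of a different prior. It does not close the point, because the section mentions no rounding, reports its one worked posterior to a tenth of a percent, and presents each entry as meeting 90% or higher.

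The second defence is that the table offers specific instances and does not claim to be complete. This stands for 2 and 3 patients: silence is not a contrary instruction, and the text rule still applies. A reader might infer that table and text give opposite decisions at 2, 3 and 70 patients as well. The documents do not support that. At 70 patients the question is also empty, because accrual to the arm is complete and the rule concerns ending accrual early.

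The third defence is that the guideline is advisory and the DSMC reviews adverse events continuously. This stands and limits the importance of the point.

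Two readings of the size should also be avoided. The rise from 6.4% to 7.8% might be attributed to the three entries, but changing those alone lowers the figure slightly; the rise comes almost entirely from 2 of 2 and 2 of 3. And the 10.4% at a true rate of 20% might be read as arms that the table misses. Most of them reach a table boundary later: overall crossing differs by about one point, 62.6% against 63.7%.

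**Conclusion.** The point holds, as a minor one. Under the stated prior and cut-off, the entries at 38, 54 and 60 patients are listed as meeting a rule that they miss by at most 0.5 percentage points. This is most plausibly because the posterior was rounded without saying so. Separately, the smallest number of patients at which the guideline applies is not stated, which leaves 2 of 2 and 2 of 3 covered by the text and absent from the table.

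Changing the three row ends alone moves the chance of crossing by 0.1 point at a true rate of 10% (6.37% to 6.30%), about 0.4 at 15% and about 0.6 at 20%. Counting the early cases as well gives a net rise over the table of 1.1 to 1.5 points across the three rates. The posterior values rest only on the plan's own prior and reference rate. The crossing probabilities also assume independent events and a check after each patient.

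**What to change.** Reconcile the table with the text of section 10.7.2 in one of two ways:
- Recompute the three row ends from the stated rule. The rows for 9, 12 and 13 events would then end at 37, 53 and 59, and the next rows would start at 38, 54 and 60. The displayed rate for 12 events would change from 22% (12/54 = 22.2%) to 23% (12/53 = 22.6%); the rates for 9 and 13 events would still round to 24% and 22%.
- Keep the table and state the rounding or cut-off that it follows.

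In either case, state the smallest number of evaluated patients at which the guideline applies, so that the cases at 2 and 3 patients are clearly in or out. The sponsor and the DSMC should decide which version is intended. No row for 70 patients is needed. The cost is a corrected table or one or two sentences, with no extra patients or data.
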